7.2. Analyses

Demographics including geographic location, HCP specialty and prescribing/dispensing of POTIGA and other AEDs will be summarized using descriptive statistics for continuous data and proportions for categorical data.

The primary outcome is the proportion of HCPs answering each question of understanding of the risks associated with POTIGA correctly. Point estimates for the proportion with correct responses, and associated 95% confidence intervals, will be calculated for each question about the awareness of risks of POTIGA. In the case of multiple choice questions, the number and proportion of subjects reporting each response will also be provided.

GSK considers a proportion (%) of correct responses of at least 80% for each individual question to represent sufficient subject understanding of the risks associated with POTIGA. This is based on previous studies by GSK including the risk management program for LAMICTAL and TREXIMET. This threshold will be imposed for prescribers and pharmacists. Prescribers and pharmacists are the HCPs who will play an important role in re-enforcing the safety messages for POTIGA.

The proportion of correct answers to survey questions will be summarized overall and by demographic subgroups. Consideration of these subgroups may highlight differences in subjects' responses. Although the sample size in some subgroups may be relatively small and have low precision, data will be grouped into 2-3 sub-categories as appropriate to identify potential trends in subject understanding including:

- Demographics (geographic location)
- Type of HCP
- POTIGA prescribing/dispensing (yes or no, months prescribing POTIGA)
- Other practice/prescribing characteristics (years in practice, years prescribing AEDs, size of patient population)

This study is descriptive; hence there will be no formal statistical testing completed.

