We would also like to confirm that you are the [INSERT: physician/pharmacist] on record for this survey. Please select one of the following options:

- 1. I affirm that I am the same [INSERT: physician/pharmacist] who was screened and sent the survey passcode. [INSERT NAME]
- 2. I am not [INSERT NAME], but I work in this [INSERT: physician's office/pharmacy].

IF PUNCH 1 (SAME PHYSICIAN/PHARMACIST), CONTINUE.

IF PUNCH 2 (NOT PHYSICIAN OR PHARMACIST, BUT WORK IN SAME OFFICE/PHARMACY), SHOW SCREEN WITH MESSAGE: 'THANK YOU FOR YOUR TIME. UNFORTUNATELY, ONLY THE HEALTHCARE PROVIDER ON RECORD MAY PARTICIPATE IN THIS STUDY. IF YOU BELIEVE YOU HAVE RECEIVED THIS MESSAGE IN ERROR, PLEASE CONTACT [INSERT NAME & PHONE #] FOR FURTHER INSTRUCTIONS.' DO NOT ALLOW SUBJECT TO CONTINUE.

Survey

The following questions are being asked about your understanding of the prescribing information and practices related only to POTIGA (ezogabine). Please respond only about this medication, based on what you know at this time.

Please take your time and read each question carefully.

Please do not guess - if you do not know the answer, please just select 'I don't know'.

1. According to U.S. prescribing information, what is the FDA-approved indication for POTIGA? (Please select all that apply)

ALLOW MULTIPLE RESPONSES, EXCEPT PUNCH 4 OR 5.

Migraine	1
Partial-onset seizures	2
Generalized tonic clonic seizures	3
None of the above	4
I don't know	5

2. True or False: According to U.S. prescribing information, POTIGA can be used as monotherapy.

ALLOW ONE RESPONSE.

True	1
False	2
I don't know	3

3. According to U.S. prescribing information, which of the following are potential risks associated with POTIGA? (Please select all that apply)

ALLOW MULTIPLE RESPONSES, EXCEPT PUNCH 5 OR 6.

Urinary retention	1
Pancreatitis	2
Ischemic colitis	3
I don't know	4

4. According to U.S. prescribing information, what is the maximum recommended daily maintenance dose of POTIGA for the General Population?

ALLOW MULTIPLE RESPONSES, EXCEPT PUNCH 5 OR 6.

600mg	1
900mg	2
1200mg	3
2000mg	4
None of the above	5
I don't know	6

5. According to U.S. prescribing information, which of the following statements, if any, is true? (Please select all that apply)

ALLOW MULTIPLE RESPONSES, EXCEPT PUNCH 5 OR 6.

The oldest age at which POTIGA can be used is 65	1
There are no lower age limits for POTIGA	2
The youngest age at which POTIGA can be used is 12	3
The youngest age at which POTIGA can be used is 18	4

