None of the above	5
I don't know	6

6. According to U.S. prescribing information, which of the following statements, if any, is true? (Please select all that apply)

ALLOW MULTIPLE RESPONSES, EXCEPT PUNCH 4 OR 5.

POTIGA should always be taken with food	1
POTIGA should always be taken on its own, without food	2
POTIGA can be taken with or without food	3
None of the above	4
I don't know	5

7. Which of the following urinary symptoms, if any, should you specifically advise patients taking POTIGA to watch out for? (Please select all that apply)

ALLOW MULTIPLE RESPONSES, EXCEPT PUNCH 5 OR 6.

Pain when urinating	1
Difficulty starting urination	2
Renal colic	3
Inability to urinate	4
None of the above	5
I don't know	6

8. If a patient on POTIGA experiences inability to pass urine, what would you advise them to do? (Please select all that apply)

ALLOW MULTIPLE RESPONSES, EXCEPT PUNCH 5 OR 6.

Report the issue at their next doctor's appointment	1
Drink more water	2
Seek immediate medical attention	3
Stop taking POTIGA	4
None of the above	5
I don't know	6

9. According to U.S. prescribing information, when increasing the dose, what is the maximum total daily dose at which POTIGA can be increased once every 7 days?

ALLOW MULTIPLE RESPONSES, EXCEPT PUNCH 5 OR 6.

Total daily dose increased by 50mg/day	1
Total daily dose increased by 150mg/day	2
Total daily dose increased by 200mg/day	3
Total daily dose increased by 300mg/day	4
None of the above	5
I don't know	6

10. True or False: According to U.S. prescribing information, for the General Population, the recommended total initial dosage should be 150mg per day for one week.

ALLOW ONE RESPONSE.

True	1
False	2
I don't know	3

11. The label for POTIGA recommends caution when prescribing for patients with which of the following conditions, if any?

		Yes	No	Don't Know
A	Moderate to severe renal or hepatic impairment	1	2	3
B	Moderate to severe Crohn's disease	1	2	3
C	Moderate to severe asthma	1	2	3
D	Patients over the age of 65 years	1	2	3
E	Moderate to severe glaucoma	1	2	3

12. True or False: It is known from controlled studies that adverse events related to voiding dysfunction generally tend to be reported within the first 6 months after starting POTIGA.

ALLOW ONE RESPONSE.

True	1
False	2
I don't know	3

13. Which of the following patient groups are recommended to have closer monitoring (including comprehensive evaluation of urologic symptoms) for urinary retention? (Please select all that apply)

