ALLOW MULTIPLE RESPONSES, EXCEPT PUNCH 6 OR 7.

Patients with benign prostatic hyperplasia (BPH)	1
Patients who are unable to communicate clinical symptoms (e.g. cognitively impaired patients)	2
Patients who use concomitant medications that may affect voiding (e.g. anti-cholinergics)	3
Patients who use non-steroidal anti-inflammatory drugs (NSAIDs)	4
Patients who are obese	5
None of the above	6
I don't know	7

SHOW SECTION B ONLY IF ANY RESPONSES (Q1-13) WERE INCORRECT

SECTION B: For the next set of questions, I'd like to ask you to provide some further information on some of your responses. Please provide as much detail of your thought process as possible when responding.

SHOW Q1_1 THROUGH Q13_1 ONLY FOR ANY INCORRECT RESPONSES AT Q1-13. THESE ARE OPTIONAL QUESTIONS. SHOW QUESTION TEXT FOR EACH, THEN THE QUESTION (1_1 – 13_1).

1_1) Previously, at Question 1, you responded [INSERT Q1 RESPONSE]. What led you to choose that response?

2_1) Previously, at Question 2, you responded [INSERT Q2 RESPONSE]. What led you to choose that response?

3_1) Previously, at Question 3, you responded [INSERT Q3 RESPONSE]. What led you to choose that response?

4_1) Previously, at Question 4, you responded [INSERT Q4 RESPONSE]. What led you to choose that response?

5_1) Previously, at Question 5, you responded [INSERT Q4 RESPONSE]. What led you to choose that response?

6_1) Previously, at Question 6, you responded [INSERT Q6 RESPONSE]. What led you to choose that response?

7_1) Previously, at Question 7, you responded [INSERT Q7 RESPONSE]. What led you to choose that response?

8_1) Previously, at Question 8, you responded [INSERT Q8 RESPONSE]. What led you to choose that response?

9_1) Previously, at Question 9, you responded [INSERT Q9 RESPONSE]. What led you to choose that response?

10_1) Previously, at Question 10, you responded [INSERT Q10 RESPONSE]. What led you to choose that response?

11_1) Previously, at Question 11, you responded [INSERT Q11 RESPONSE]. What led you to choose that response?

12_1) Previously, at Question 12, you responded [INSERT Q12 RESPONSE]. What led you to choose that response?

13_1) Previously, at Question 13, you responded [INSERT Q13 RESPONSE]. What led you to choose that response?

SKIP TO DEMOGRAPHICS (B) IF QA = PUNCH 4 OR 5. CONTINUE TO DEMOGRAPHICS (A) IF QA = PUNCH 1, 2 OR 3.

DEMOGRAPHICS (A)

The next sets of questions are about your practice history so that we can group your responses with others like you.

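### Q3, the one item that asks directly whether urinary retention is a POTIGA risk, makes exclusive two response codes it does not have, so *I don't know* can be recorded together with *Urinary retention*

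*Protocol*

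**What the plan says.** Section 7.2 defines the outcome item by item: "The primary outcome is the proportion of HCPs answering each question of understanding of the risks associated with POTIGA correctly". The same section takes at least 80% correct on each question as sufficient understanding. No answer key or rule for mixed answers appears in the protocol.

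In Section 11.2, Q3 reads "According to U.S. prescribing information, which of the following are potential risks associated with POTIGA? (Please select all that apply". Its options are urinary retention (1), pancreatitis (2), ischemic colitis (3) and *I don't know* (4). The note beneath it is "ALLOW MULTIPLE RESPONSES, EXCEPT PUNCH 5 OR 6". The introduction to the survey tells respondents: "Please do not guess - if you do not know the answer, please just select 'I don't know".

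Three smaller places in the same section belong with this:

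- Q4 asks for one maximum daily dose and Q9 asks "what is the maximum total daily dose at which POTIGA can be increased once every 7 days". Neither invites several answers, but both carry the multiple-response note.
- Item 5_1 reads "Previously, at Question 5, you responded [INSERT Q4 RESPONSE]. What led you to choose that response".

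**The concern.** An exclusivity note exists to stop a respondent from combining a substantive answer with an opt-out. In Q3 it guards two codes that are absent and leaves the opt-out that is present unguarded. A record with both *Urinary retention* and *I don't know* contradicts itself, and the protocol does not say whether it is correct.

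The item matters because it is the only one that asks whether urinary retention is a risk at all. Q7, Q8, Q12 and Q13 ask about symptoms, advice, timing and monitoring, and presuppose a urinary problem. At 200 respondents per group, 80% is 160 correct answers, so every two mixed records move Q3 by one percentage point if the scoring rule changes.

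Q3 also gives no truthful answer to a respondent who believes that none of the three listed conditions is a risk.

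**Working it through.** **Step 1. Option lists against exclusivity notes (Section 11.2).** All multi-response knowledge items:

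| Item | Punches listed | *None of the above* | *I don't know* | Exclusive per note | Match |
|---|---|---|---|---|---|
| Q1 | 1–5 | 4 | 5 | 4, 5 | yes |
| Q3 | 1–4 | absent | 4 | 5, 6 | **no** |
| Q4 | 1–6 | 5 | 6 | 5, 6 | yes |
| Q5 | 1–6 | 5 | 6 | 5, 6 | yes |
| Q6 | 1–5 | 4 | 5 | 4, 5 | yes |
| Q7 | 1–6 | 5 | 6 | 5, 6 | yes |
| Q8 | 1–6 | 5 | 6 | 5, 6 | yes |
| Q9 | 1–6 | 5 | 6 | 5, 6 | yes |
| Q13 | 1–7 | 6 | 7 | 6, 7 | yes |

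The notes are adapted to the list elsewhere ("ALLOW MULTIPLE RESPONSES, EXCEPT PUNCH 4 OR 5" under Q1 and Q6, "ALLOW MULTIPLE RESPONSES, EXCEPT PUNCH 6 OR 7" under Q13). Only Q3 fails: {5, 6} and {1, 2, 3, 4} share no member. The Q3 list is numbered without a gap, so this is not text lost in extraction.

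**Step 2. The plan's own precision figure (Section 8).** The margin is 1.96 × √(p(1 − p)/n). With p = 0.80 and n = 200 it is 1.96 × √(0.16/200) = 5.54 points. The stated 5.5 is reproduced.

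**Step 3. Mixed answers.** Assume 80% of 200 tick urinary retention, and a share c of all respondents tick it together with *I don't know*. The protocol gives no value for c; 1% to 10% is an assumed range.

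| c | Records | Any tick of punch 1 correct | Mixed record not correct |
|---|---|---|---|
| 1% | 2 | 80% | 79% |
| 2% | 4 | 80% | 78% |
| 5% | 10 | 80% | 75% |
| 10% | 20 | 80% | 70% |

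Had punch 4 been exclusive, each of these respondents would have had to choose between the two, and the rate would lie between 80% − c and 80%. Against that, lenient scoring can overstate by 0 to c points and strict scoring can understate by 0 to c points. The sign depends on the rule.

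**Step 4. Missing *None of the above*.** Anyone who would choose it is wrong on Q3. Without it, that person gives another wrong answer (no change) or ticks urinary retention (possible rise). With f the share affected and g the fraction who then score correct, the rise is f × g, which cannot be negative. If all choose *I don't know*, g = 0 and the rise is 0. If f is 5% to 10% and they pick one of the four options at random, it is 0.05 × 0.25 = 1.25 to 0.10 × 0.25 = 2.5 points. Both f and g are assumptions.

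**The case against.** The strongest reply is that this is a slip in a programming note. The scoring rule may sit in an analysis plan that is not shown. If it requires an exact match, mixed answers are already wrong and cannot inflate the rate. This stands as to direction. A reader might infer that the fault pushes the Q3 rate up; the protocol does not support that, because strict scoring removes any gain from mixed answers and may lower the rate.

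The reply does not dispose of the note itself. Option lists and exclusivity codes are fixed in this questionnaire. Section B opens only for incorrect responses, so the survey program has to classify a mixed answer while the respondent is still answering. The pilot was to be done by telephone (Section 3.1), while about 85% were expected online, so it may not have tested the online logic.

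On the missing option, the instruction not to guess points such respondents to an answer that is also not correct, so the effect may be nil. Physicians must also have prescribed POTIGA in the past 12 months (Section 4.2.1), which makes a large share of them believing that none of the options is a risk less plausible. Both points stand against any firm estimate of inflation. They do not alter the one-sidedness shown in Step 4.

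Q4, Q9 and 5_1 concern dose and age, outside the urinary-retention outcome of Section 5.2. A reader might infer that every explanation given at 5_1 is about the wrong question. That goes too far: the item is optional, the question text is shown first and the prompt names Question 5. Only the inserted answer is wrong.

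**Conclusion.** The point holds as an error of specification. Q3's exclusivity note does not fit its options, and contradictory answers can be recorded on a primary-outcome item judged at 80%. This assumes the survey was programmed as the note is written.

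The effect of mixed answers has unknown size and takes its sign from a scoring rule not stated in the protocol. The absence of *None of the above* can only leave the rate as it is or raise it, by an amount not computable from the document. The figures in Steps 3 and 4 illustrate assumed shares and are not estimates. The errors at Q4, Q9 and 5_1 are minor.

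This is a correction worth making because it is nearly free. Nothing in the protocol shows that it endangers the study's conclusion.

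**What to change.** 1. **Q3 note:** make punch 4 the exclusive code in place of 5 and 6.
2. **Scoring:** state that any Q3 record combining *I don't know* with another option is not correct, and apply this to records already collected. Report how many such records there are, since the option-by-option counts promised in Section 7.2 do not show combinations.
3. **5_1:** insert the Q5 response instead of the Q4 response.
4. **Q4 and Q9:** allow one response each.

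The cost is a few lines of programming and one scoring sentence. The strict rule may slightly understate understanding, by at most the share of mixed records.

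Adding *None of the above* to Q3 is optional. Sections 3.2 and 5.1 show that the study had already started, and that physician recruitment was running low. A new option would create two versions of Q3. If 200 respondents split evenly between them, Table 1 gives a margin of ±8.0 points at n = 100 and 80% correct, against ±5.5 at n = 200. If the option is not added, its absence should be named as a limitation when Q3 is reported.

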5.2. Outcomes

Subject understanding of the risk of urinary retention and the symptoms of acute urinary retention associated with POTIGA will be assessed using the survey instrument.

The primary outcome of this study is the proportion of subjects that correctly respond to individual survey questions concerning the risk of urinary retention and the symptoms of acute urinary retention associated with POTIGA. The order in which potential responses to survey questions appear will be randomized. The proportion responding correctly will be tabulated separately for each item in the subject understanding survey instrument. These risks represent those described in the DHCP letter.

At the conclusion of the online survey, the final screen will display a summary of the relevant information from the POTIGA prescribing information, and a link to <http://www.potiga.com>. The phone respondents will be offered materials by email or the POTIGA website, but will also be given the toll-free number for the POTIGA response center [name] ([name]).

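### Questionnaire items Q4 and Q9 each ask for one maximum but are programmed to accept several doses, so their answers and their percent correct are ambiguous

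*Protocol*

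**What the plan says.** All the items are in the Protocol, section 11.2 (Questionnaire).

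- Q4 asks "what is the maximum recommended daily maintenance dose of POTIGA for the General Population" and lists four doses, then a none-of-these option (punch 5) and a don't-know option (punch 6).
- Q9 asks "what is the maximum total daily dose at which POTIGA can be increased once every 7 days" and lists four increments, then the same two closing options.
- Both carry the note "ALLOW MULTIPLE RESPONSES, EXCEPT PUNCH 5 OR 6". Only punches 5 and 6 are exclusive; punches 1 to 4 may be combined freely.
- The other dosing item, Q10, asks whether it is true that "the recommended total initial dosage should be 150mg per day for one week", and is limited to one response. So are Q2 and Q12.
- Before Q1 the respondent reads: "Please do not guess - if you do not know the answer, please just select 'I don't know".
- After Q13 the programme is told: "SHOW SECTION B ONLY IF ANY RESPONSES (Q1-13) WERE INCORRECT". Each respondent's answers must therefore be classed as right or wrong while the survey is running.

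Section 5.2 defines the primary outcome on "individual survey questions concerning the risk of urinary retention and the symptoms of acute urinary retention associated with POTIGA" and adds that the proportion correct is tabulated item by item. Section 7.2 takes "at least 80% for each individual question to represent sufficient subject understanding", and the same sentence goes on to tie that understanding to the risks of the drug. Section 7.2 also promises the number and proportion choosing each response on multiple-choice questions.

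**The concern.** A maximum is one number, so the four doses in each list exclude one another. A respondent who ticks 600, 900 and 1200 mg at Q4 has not stated a maximum, yet the instrument accepts the answer. The loss happens at data capture: no later analysis can recover which figure the respondent believed. Section 3.1 bars telephone interviewers from departing from the script or adding instructions, so they cannot ask for a single choice either.

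At stake is the item-level result for Q4 and Q9. Its value depends on how a set of doses containing the keyed one is classified (the keyed option being the one the sponsor's answer key treats as correct). The same classification decides who is shown probes 4_1 and 9_1.

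**Working it through.** **1. Comparison of items.** Stem and programming for the knowledge items Q1 to Q13, leaving aside the yes/no grid at Q11:

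| Items | Stem invites several ticks | Programming |
|---|---|---|
| Q2, Q10, Q12 | no | one response |
| Q1, Q3, Q5–Q8, Q13 | yes | several responses |
| Q4, Q9 | no | several responses |

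Only Q4 and Q9 pair a single-answer stem with multiple-response programming. Q3 carries the same note about punches 5 and 6 but has only four options. That suggests the note was copied from item to item, though this is an inference.

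**2. The plan's own precision figure.** Section 8 gives ±5.5 points for 80% correct and n = 200. Check: 1.96 × √(0.8 × 0.2 / 200) = 1.96 × 0.02828 = 0.0554, or 5.54 points. The figure reproduces. It serves here only as a yardstick.

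**3. How many answers are ambiguous.** Four combinable doses give 2⁴ − 1 = 15 non-empty patterns. Assume the keyed option is one of the four.

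- Patterns containing it: 2³ = 8.
- Patterns consisting of it alone: 1.
- Patterns whose status depends on the scoring rule: 8 − 1 = 7.

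If the keyed option were punch 5, which is exclusive, the two rules would agree on every pattern. These are counts of patterns, not probabilities of behaviour.

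**4. What each rule does.** Let K be the share who know the figure and tick it alone, and m the share of the rest who tick several doses including the keyed one. Suppose nobody else is scored correct. Then:

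- any tick of the keyed dose counts: observed = K + (1 − K)m;
- keyed dose must stand alone: observed = K, so there is no inflation from multiple ticks.

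For K = 70%, with K and m both assumed:

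| m | any-tick rule | sole-selection rule | difference |
|---|---|---|---|
| 10% | 73.0% | 70.0% | 3.0 points |
| 25% | 77.5% | 70.0% | 7.5 points |
| 50% | 85.0% | 70.0% | 15.0 points |

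In head-count terms, each ambiguous respondent in a group of 200 moves the item by 1/200 = 0.5 points, so 4 would move it by 2 points and 10 by 5 points. The documents give no rate from which to choose among these values.

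**The case against.** A reader might infer that people who tick a range of doses will be counted as knowing the limit. The protocol does not support this. It states no any-tick rule, and a scoring key may properly sit in an analysis plan that is not shown, so the missing key is not itself a fault. Under sole-selection scoring a range earns no credit, and the format is then stricter than a single-response one: a randomly chosen pattern matches the keyed dose alone 1 time in 15 (7%), against 1 in 4 (25%) for a blind single guess.

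A reader might also infer that an item could be carried over the 80% line and alter the survey's conclusion. That is not supported either. The threshold in section 7.2 is tied to understanding of risks, and the primary outcome in section 5.2 to urinary retention and its symptoms. Q4 and Q9 concern dosing.

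Three further points count on the other side:

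- Q5 and Q6 also list options that exclude one another and also accept several. What sets Q4 and Q9 apart is that their stems do not invite multiple ticks.
- That wording, the request not to guess and the don't-know option should make multiple ticking uncommon.
- Response proportions that sum to more than 100% are ordinary for multiple-response items, and on Q4 or Q9 would themselves reveal that multiple ticking had occurred.

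These limit the consequence but do not remove the mismatch. A contradictory answer stays uninterpretable under any scoring rule, and the live routing after Q13 must still classify it.

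**Conclusion.** The point holds as a small defect of the instrument. Q4 and Q9 ask for one maximum and accept several, and where that happens the answer has no clear meaning and its correct or incorrect status is not settled in the protocol. Percent correct would be inflated if any tick of the keyed option counted, and would not be inflated if that option had to stand alone.

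The size of any effect is unknown. The differences of 3 to 15 points in the working rest on assumed values of K and m and on the any-tick rule, and they apply only if a listed dose is the keyed option. What may be affected is the item-level reporting of these two questions and the routing to their probes. No effect on the primary outcome or on the 80% criterion is shown. No view is taken on which dose is right.

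**What to change.** Replace the programming note on Q4 and Q9 with the one-response note already used on Q2, Q10 and Q12.

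For interviews completed before the change, add one scoring sentence: the item is correct only if the keyed option is the sole selection. Report, for each item and for prescribers and pharmacists separately, how many respondents selected more than one dose. The per-option totals cannot supply this count, because a respondent who ticks three doses adds two to the excess.

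The cost is two programming notes and one sentence. There is a small downside. Sections 3.2 and 5.1 record changes made after the study began, so a change now may mix two response formats within each item, and percent correct may come out slightly lower. If reprogramming in the field is not acceptable, the scoring sentence and the count of multiple ticks alone would settle how answers are classified, though not what the contradictory answers mean.

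### Questionnaire item Q9 asks for a dose level but offers only dose increments, so a low score would mix item wording with lack of knowledge (minor)

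*Protocol*

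**What the plan says.** Q9 in Section 11.2 asks "when increasing the dose, what is the maximum total daily dose at which POTIGA can be increased once every 7 days". Its numeric options are "Total daily dose increased by 50mg/day", "Total daily dose increased by 150mg/day", "Total daily dose increased by 200mg/day" and "Total daily dose increased by 300mg/day", followed by none-of-the-above and don't-know options.

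Two other items also deal with dose amounts. Q4 asks "what is the maximum recommended daily maintenance dose of POTIGA for the General Population" and offers totals from 600 to 2000 mg. Q10 is a true/false statement that "for the General Population, the recommended total initial dosage should be 150mg per day for one week". Both name the General Population; Q9 names no population.

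Q9 is a scored item: the programming note after Q13 opens Section B when any answer to Q1 to Q13 is incorrect, and probe 9_1 then asks what led to the Q9 response. Section 5.2 tabulates the proportion correct separately for each item. The appendix shows no answer key.

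**The concern.** The stem and the options refer to different quantities. A total daily dose is a level, as in Q4, which respondents have answered shortly before. An amount by which the total is raised is a step. None of the four numeric options is a level, so a literal reader has grounds to conclude that no listed answer fits.

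The survey's own rules leave little room to repair this. The questionnaire tells respondents to read carefully and not to guess. Section 3.1 forbids telephone interviewers from adding information or instructions, and about 85% of respondents are expected to answer online with no interviewer at all.

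At stake is the interpretation of one item. If Q9 scores low, the proportion correct alone would not show whether respondents did not know the titration step or answered the question as worded.

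**Working it through.** **1. Stem against options.**

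| Item | Quantity in the stem | Quantity in the options | Population named |
|---|---|---|---|
| Q4 | Maximum daily maintenance dose (level) | Levels, 600 to 2000 mg | General Population |
| Q9 | Maximum total daily dose (level) | Increments of 50, 150, 200 or 300 mg/day | None |
| Q10 | Total initial dosage (level) | True/false on a stated level | General Population |

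In Q4 and Q10 the stem and the answers concern the same quantity. In Q9 they do not. Q9 also allows several responses although a maximum has a single value; Q4 is programmed the same way.

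**2. Scoring consequence.** Assume the keyed answer is one of the four increments (no key is shown). A literal reader who knows the step but chooses none of the above, or don't know, is then not counted as correct. Let K be the share who know the step and m the share of those who lose the mark through the wording. Ignoring lucky guesses,

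observed proportion correct = K × (1 − m).

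The error runs in one direction and does not shrink with sample size.

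**3. Can it be sized?** No. The protocol gives neither K nor m. Purely as an illustration with assumed K, the observed share drops below 80% once m exceeds 1 − 0.80/K:

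- K = 85%: 1 − 0.80/0.85 = 5.9%
- K = 90%: 1 − 0.80/0.90 = 11.1%
- K = 95%: 1 − 0.80/0.95 = 15.8%

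At m = 10% the observed shares would be 76.5%, 81.0% and 85.5%. With smaller losses the 80% mark can survive: 0.85 × 0.95 = 80.75%, and 0.89 × 0.90 = 80.1%. These figures show how the result depends on the assumptions; they do not estimate the effect.

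**4. Population wording.** Q11 offers "Moderate to severe renal or hepatic impairment" and age over 65 among possible caution groups. It asks about caution, not about titration. Nothing in the protocol says that the titration step differs by population.

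**5. Precision if results are split by wording.** The Wald half-width is 1.96 × √(p(1 − p)/n). With p = 0.80 and n = 200 it is 1.96 × √(0.16/200) = 5.5 points, which reproduces the figure in Section 8. With n = 100 it is 1.96 × √(0.16/100) = 7.8 points, shown as 8.0 in Table 1.

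**The case against.** The strongest reply is that the literal reading is strained. The stem speaks of increasing the dose once every 7 days, and every numeric option says that the total is increased by some amount. A respondent who knows the step has strong cues to the intended meaning. This stands, and it is the main reason to rate the effect as minor.

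The plan also has partial safeguards. Section 7.2 already reports the proportion choosing each response to multiple-choice questions, so the none-of-the-above share will be visible. Probe 9_1 could reveal misreading. The pilot in Section 3.1 was meant to improve clarity. These help but do not cure the item: the probe is optional and free text, no rule re-scores Q9 from it, and the mismatch is still in the questionnaire.

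Q9 also lies outside the primary outcome, which Sections 2 and 5.2 define on urinary retention risk and the symptoms of acute urinary retention. Section 7.2 ties the 80% threshold to questions on understanding of the risks. A reader might infer that the wording puts the primary outcome in doubt; the protocol does not support that.

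**Conclusion.** The mismatch between Q9's stem and its options is plain on the page and worth correcting. A respondent who reads the stem literally could be scored wrong for a defensible answer, so a low Q9 result should not be taken by itself as a knowledge gap. The effect is minor and confined to one scored dosing item. The conclusion assumes that the key is one of the increments and that some informed respondents read literally; how many do so is unknown.

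Two stronger readings are tempting, and the protocol supports neither. One is that the wording would pull Q9 below 80%. That needs a misreading rate and a true level of knowledge that the protocol does not give, and it is not clear that the threshold governs this item. The other is that the missing General Population limit causes mis-scoring. It could do so only if the titration step differed by population, which the protocol does not say. That half is a wording inconsistency to check.

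**What to change.** - Reconcile Q9's stem with its response options, in the online program and the telephone script, so that both refer to the amount of each increase. The options and the answer key stay with the sponsor; this review takes no view on which dose is right.
- Have the sponsor check whether the General Population limit in Q4 and Q10 is meant to apply to Q9, and word Q9 accordingly.
- Sections 3.2 and 5.1 show that the study had already started. If responses were collected under the present stem, report Q9 by wording version. Do not read a low result under the present stem as a knowledge gap without looking at the none-of-the-above share and the 9_1 answers.

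The edit is one stem and no new tabulation of responses is needed. The cost is precision for Q9 within each wording version: a group of 200 split evenly has about ±8 points per version at 80% correct, instead of ±5.5. With recruitment of prescribing physicians already slower than expected (Section 3.2), that loss is real, but it touches only this item.
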